### **13.4 Analysis of Primary Endpoints**

The primary analysis of the study will be the comparison of PFS per RECIST 1.1 between Arm A and Arm B using logrank test and group sequential methods to control the overall one-sided Type I error rate at 0.1.

The null and alternative hypotheses are defined using the hazard ratio (HR) of the Arm A to Arm B as:

$$\begin{aligned} H_0: & \text{ HR} \leq 1 \\ H_1: & \text{ HR} > 1 \end{aligned}$$

All inferences will be conducted in the intent-to-treat manner, and the survival function will be summarized using the Kaplan-Meier methods according to randomized treatment assignment. Final analysis will be performed after 70 PFS events are observed or at least 12 months after the last patient is enrolled on study, whichever occurs first.

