### **3.1 Eligibility Criteria**

3.1.1 Patients must have histologically or cytologically confirmed Stage IV invasive breast cancer. Patients without pathologic or cytologic confirmation of metastatic disease should have unequivocal evidence of metastasis from physical examination or radiologic evaluation.

- 3.1.2 Subjects must have at least one lesion that is not within a previously radiated field that is evaluable on computerized tomography (CT) or magnetic resonance imaging (MRI) scan per RECIST version 1.1. If the subject's only evaluable disease is within a previously radiated field, it must have demonstrated progression since the time of radiation.
- 3.1.3 Participants must have HR positive, HER2-negative breast cancer (ER>1% and/or, PR>1%, HER2-negative per ASCO CAP guidelines, 2013 resulted on the primary tumor and/or a metastatic lesion).
- 3.1.4 Participants must have already received or been intolerant to at least two lines of hormonal therapies (including the adjuvant or metastatic setting) or be appropriate candidates for chemotherapy
- 3.1.5 **Prior chemotherapy:**  
Participants are allowed to have received up to 2 prior lines of chemotherapy in the metastatic setting. If a prior chemotherapy was given for less than 1 cycle, it will not be counted as a prior line. The last dose of chemotherapy must be  $\geq$ 14 days prior to initiation of study therapy. Participants should be adequately recovered from acute toxicities of prior treatment. No prior treatment with eribulin mesylate is allowed.
- 3.1.6 **Prior biologic therapy:** The last dose of biologic or investigational therapy must be  $\geq$ 21 days prior to initiation of study therapy.
- 3.1.7 **Prior hormonal therapy:** Hormonal therapy must have been discontinued  $\geq$ 14 days prior to initiation of study therapy. However, continuation of ovarian suppression is allowed.
- 3.1.8 **Prior radiation therapy:** Participants may have received prior radiation therapy in either the metastatic or early-stage setting. Radiation therapy must be completed  $\geq$ 14 days prior to initiation of study therapy.
- 3.1.9 **Prior targeted therapy:** Targeted therapy must have been discontinued  $\geq$  14 days prior to initiation of study therapy.
- 3.1.10 **Biphosphonates/Denosumab:** Participants on bisphosphonates/denosumab may continue receiving bisphosphonate therapy during study treatment.

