## **13. STATISTICAL CONSIDERATIONS**

### **13.1 Study Design/Endpoints**

This is a randomized phase II open label study of eribulin mesylate +/- Pembrolizumab for patients with metastatic HR positive breast cancer treated with 0-2 line of chemotherapy. Eighty-eight patients will be randomized (1:1) to eribulin mesylate with pembrolizumab or eribulin mesylate. Patients randomized to eribulin mesylate monotherapy will have the option to receive pembrolizumab monotherapy at time of progression.

The primary endpoint is PFS, defined as the time from study randomization to disease progression per RECIST 1.1 or death due to any cause, whichever occurred first. Patients alive without disease progression are censored at the date of last disease evaluation. The primary objective is to compare PFS of patients randomized to receive eribulin mesylate in combination with pembrolizumab (Arm A) versus those randomized to receive eribulin mesylate monotherapy (Arm B).

Secondary endpoints include PFS per irRECIST criteria, ORR per RECIST 1.1 and irRECIST, DOR, CBR, OS, safety and tolerability. For the patients randomized to the eribulin monotherapy arm who elect to receive the combination after progression, we will also perform an exploratory analysis of all clinical endpoints for patients using measurements at progression on monotherapy as the baseline tumor assessment.

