### **13.2 Sample Size, Accrual Rate and Study Duration**

The target accrual is 88 patients (44 in eribulin mesylate alone arm and 44 in eribulin mesylate+pembrolizumab combination arm). The study has 83% power to distinguish a 3 month improvement in PFS from 4.1 to 7.1 months (HR = 0.58) with a one-sided alpha of 0.1. This statement of power assumes a final analysis when 70 PFS events are observed, and would be anticipated to occur after a constant accrual over 18 months with 6 months of additional follow-up. Further assumptions are a constant hazard of PFS and dropout such that 5% of patients are lost-to-follow-up at 1 year. This allows for one futility analysis at 50% information (35 PFS

events) and would stop early if the Z-statistics from the logrank test is less than 0 (i.e. observed HR from a Cox model  $> 1.0$ ).

The expected accrual rate is 3-5 patients per month, and the accrual is expected to complete within 18-24 months.

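### Improvement, not an error: the primary PFS test is unadjusted although patients with 0, 1 or 2 prior metastatic chemotherapy lines are enrolled; pre-specifying adjustment for prior lines is cheap and protects power if line is prognostic

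*Combined protocol and SAP*

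**What the plan says.** Section 13.4 has the arms compared on PFS per RECIST 1.1 "using logrank test and group sequential methods", and holds the one-sided error rate to 10% overall. It names no stratification factor and no covariate.

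Section 13.1 describes allocation only by its ratio: "Eighty-eight patients will be randomized (1:1) to eribulin mesylate with pembrolizumab or eribulin mesylate". Sections 1.1, 4.1 and 5.1 add no stratification factor.

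Section 3.1.5 fixes the population: "Participants are allowed to have received up to 2 prior lines of chemotherapy in the metastatic setting". Section 4.1 has the eligibility checklist completed before the registrar randomizes the patient.

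Section 13.2 gives the design. Its power claim reads "The study has 83% power to distinguish a 3 month improvement in PFS". The control and target medians are 4.1 and 7.1 months, a hazard ratio of 0.58, and the test is run "with a one-sided alpha of 0.1". The calculation presumes "a final analysis when 70 PFS events are observed" and also a constant PFS hazard. One futility look at 35 events uses the same logrank Z, with a cut at 0.

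**The concern.** The population definition mixes patients starting their first, second or third line of chemotherapy for metastatic disease. If PFS shortens with each prior line, each arm is a mixture of hazards. An unadjusted logrank test then estimates a treatment effect that is diluted relative to the effect within a line, and its power falls below the figure calculated for one constant hazard per arm.

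The second issue is chance imbalance. With 44 patients per arm and no stratification described, one arm can end up with noticeably more pretreated patients, and the planned test has no means of correcting for it. Adjusting after such an imbalance has been seen would be post hoc, so the choice has to be made in advance. The futility rule uses the same statistic at half the events, where the estimate is less precise.

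**Working it through.** **1. The plan's own power.** Inputs from Section 13.2: 70 events, one-sided alpha 0.1 (z = 1.2816), 1:1 allocation, HR = 4.1/7.1 = 0.5775 (stated as 0.58).

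- Schoenfeld: Φ(√70/2 × |ln HR| − 1.2816). For 0.5775: Φ(4.183 × 0.549 − 1.2816) = Φ(1.016) = 84.5%. For 0.58: 84.1%.
- Freedman: Φ(√70 × (1 − HR)/(1 + HR) − 1.2816). For 0.5775: Φ(8.367 × 0.2678 − 1.2816) = Φ(0.959) = 83.1%. For 0.58: 82.7%.
- Schoenfeld with the futility stop at Z < 0 at 35 events always obeyed: 83.0% (0.5775) or 82.6% (0.58).

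Expected events at 24 months are 69.9. The stated 83% and 70 events both reproduce.

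**2. Chance of imbalance.** Assume half the patients have 0 prior lines. The SD of the difference in shares between arms is √(0.25 × 2/44) = 10.7 points. The chance of a difference above 15 points is 2 × (1 − Φ(15/10.7)) = 2 × (1 − Φ(1.41)) ≈ 16%.

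**3. Average power, simulated.** Inputs from the plan: 88 patients, 18-month accrual, 5% per year dropout, analysis at 70 events, within-stratum treatment HR 0.5775. Assumptions: randomization not stratified, no interim stop, a two-level factor (0 vs 1-2 lines), a 50:50 mix, and the prognostic HRs in the first column.

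| Prognostic HR, 1-2 vs 0 lines | Unstratified logrank | Stratified logrank | Cox score test, prior lines as covariate |
|---|---|---|---|
| 1.0 | 84.2% | 83.5% | 84.2% |
| 1.5 | 82.1% | 83.0% | 83.5% |
| 2.0 | 80.3% | 83.0% | 83.9% |

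A separate run with equal groups gave 77% unstratified against 83% stratified at HR 2.5. With one third at 0 lines and two thirds at 1-2, unstratified vs stratified power was 83.9% vs 83.0% (HR 1.0), 82.5% vs 82.8% (1.5) and 79.9% vs 82.3% (2.0).

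**4. Three strata (0, 1, 2) are less attractive.** With equal thirds, unstratified vs stratified power was about 83.6% vs 81.7% if line is not prognostic, about equal at 1.35-fold hazard per line, 80.2% vs 81.9% at 1.5-fold and 73.6% vs 81.9% at 2.0-fold. Splitting 70 events over three strata costs up to about 2 points.

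**5. Type I error.** Under no treatment effect, in the three-strata setting with unstratified randomization, both logrank tests rejected in 10.1% to 10.3% of trials.

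**6. What imbalance does when it occurs.** A 15-point imbalance moves the unadjusted log HR by roughly 0.15 × ln 1.5 = 0.06, or 0.15 × ln 2 = 0.10. The standard error with 70 events is about 2/√70 = 0.24, so the shift is 0.25 or 0.43 of a standard error. Simulation restricted to trials with imbalance of about 15 points or more (50:50 mix) gave:

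| Condition | Prognostic HR | Unstratified | Stratified |
|---|---|---|---|
| Power, more pretreated patients in the combination arm | 1.5 | 74% | 84% |
| Power, same direction | 2.0 | 63% | 82% |
| False-positive rate, imbalance favouring the combination | 1.5 | 18% | 10% |
| False-positive rate, same direction | 2.0 | 23% | 11% |

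Each direction accounts for about half of the 16%. Over all randomizations the two directions offset each other, which is why the overall error rate stays near 10%.

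**The case against.** The strongest reply is that nothing here is broken. An unadjusted logrank test is valid, its Type I error already allows for chance imbalance, and the stated power is right for the model stated. This stands in full.

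A reader might infer that the trial is underpowered as planned, or that stratifying necessarily recovers power. The documents support neither reading. They report no PFS by number of prior lines, no hazard ratio per line and no expected mix. At a moderate prognostic HR of 1.5 the average gain is 0-1 point, close to simulation noise. If the factor is not prognostic, stratifying loses about 1 point. Gains of several points need a prognostic HR of 2 or more, which no section supports.

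A reader might also take it as stated that prior lines are a recorded data field and that allocation is simple randomization. Both are inferences. Eligibility requires the count to be known, but no section names a case report form field for it, and no section describes the randomization method beyond the 1:1 ratio.

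Finally, 0 versus 1-2 lines still pools the second- and third-line patients, and the documents do not rank prior lines above other baseline factors. The two-level split is a compromise that limits the cost shown in step 4. Prior lines are chosen because the eligibility rule builds that heterogeneity into the population.

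These points limit the claim to a modest one. They do not remove it: the worst case is about 1 point of power, and in the simulation covariate adjustment avoided even that.

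**Conclusion.** The concern holds as an efficiency and robustness improvement, not as an error. The 83% power and the one-sided 10% error rate are correct as planned.

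If prior line is prognostic, the unadjusted test gives up some average power. For 0 versus 1-2 lines, stratifying changes power by about −1 point (not prognostic), 0 to +1 (HR 1.5), +2 to +3 (HR 2.0) and +5 to +6 (HR 2.5). It also makes the answer much less dependent on line mix in the roughly one trial in six (50:50 mix) where the arms differ by more than 15 points.

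All gains rest on an assumed prognostic effect and an assumed mix of lines.

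**What to change.** In Section 13.4, before any outcome data are seen, pre-specify a primary PFS comparison adjusted for prior chemotherapy lines for metastatic disease (0 vs 1-2). Two forms are suitable:

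- a stratified logrank test, with the HR from a Cox model stratified the same way; or
- the treatment test from a Cox model with prior lines as a covariate, which showed no loss in simulation when the factor was not prognostic.

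Use the same statistic for the futility Z in Section 13.2, so that the cut at 0 corresponds to an adjusted HR of 1. Keep the unstratified logrank as a sensitivity analysis. State the prognostic effect and mix assumed, and confirm that the number of prior lines is captured as a data field.

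The cost is a few sentences of statistical text and, if not already present, one baseline field. No extra patients, visits or scans are needed. The downside is about 1 point of power with the stratified logrank if line turns out not to be prognostic.

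### Section 13.4 prints the primary hypotheses in the wrong direction: with HR taken as Arm A over Arm B, the alternative HR > 1 is harm from the combination

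*Combined protocol and SAP*

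**What the plan says.** Section 13.4 gives the formal hypotheses for the primary PFS comparison: "The null and alternative hypotheses are defined using the hazard ratio (HR) of the Arm A to Arm B as". The two displayed lines that follow are H0: HR ≤ 1 and H1: HR > 1. The test is a log-rank test with one-sided type I error of 0.1.

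Section 13.1 fixes the labels and the endpoint. It compares patients "randomized to receive eribulin mesylate in combination with pembrolizumab (Arm A) versus those randomized to receive eribulin mesylate monotherapy (Arm B"), and PFS is "defined as the time from study randomization to disease progression per RECIST 1.1 or death due to any cause, whichever occurred first".

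Section 13.2 gives the design: "The study has 83% power to distinguish a 3 month improvement in PFS", from a median of 4.1 to 7.1 months, HR = 0.58, "with a one-sided alpha of 0.1". It adds: "This statement of power assumes a final analysis when 70 PFS events are observed". It also sets the futility rule: stop at 35 events if the log-rank Z is below 0, which it equates with an observed Cox HR above 1.0. Section 13.3 describes that boundary as no difference or a worse result with the combination, and speaks of concluding superiority at the final analysis.

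**The concern.** The event is unfavourable, so a hazard ratio of Arm A to Arm B above 1 means earlier progression or death on the combination. As printed, the hypothesis to be established is harm, and any benefit, including the design value of 0.58, belongs to the null.

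In a one-sided test the direction decides which tail is the p-value. Section 13.4 is the only place where the formal primary hypotheses are written. A program, table shell or report built from it alone would report 1 − p in place of p. A result exactly at the intended success limit (p = 0.10) would appear as p = 0.90.

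**Working it through.** **Inputs.** HR orientation Arm A / Arm B and the printed signs (13.4); arm labels and event (13.1); medians 4.1 and 7.1 months, HR 0.58, 70 final events, one-sided alpha 0.1, 44 patients per arm, futility look at 35 events with stop if Z < 0 (13.2); futility non-binding and no early stop for efficacy (13.3). Because there is no efficacy look and futility is non-binding, the final critical value is the ordinary one-sided z = 1.2816.

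**Step 1. Orientation of the design HR.** Under the constant hazard assumed in 13.2, HR(A/B) = 4.1/7.1 = 0.577, which the plan rounds to 0.58. Sections 13.2 and 13.4 therefore use the same orientation. Read as B to A, the ratio would be 7.1/4.1 = 1.73, which appears nowhere.

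**Step 2. Reproduce the stated 83%, rejecting for HR < 1.** Drift at HR 0.58 is 0.5447 × √(70/4) = 0.5447 × 4.183 = 2.279.

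| Method | HR 0.577 | HR 0.58 |
|---|---|---|
| Schoenfeld: Φ(drift − 1.2816) | 84.5% | 84.1% |
| Freedman: Φ(√70 × (1 − HR)/(1 + HR) − 1.2816) | 83.1% | 82.7% |
| Schoenfeld drift, Z < 0 stop at 35 events obeyed (bivariate normal, correlation √0.5) | 83.0% | 82.6% |

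The plan's figure is recovered with rejection for HR < 1. A two-sided 0.1 test would give about 74%, which does not match.

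**Step 3. The test as printed.** It rejects H0: HR ≤ 1 only if the observed HR exceeds exp(2 × 1.2816/√70) = 1.36. At a true HR of 0.58:

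- P(reject) = Φ(−1.2816 − 2.279) = Φ(−3.561) = 0.0002.
- If the futility stop is also obeyed, the probability falls to about 0.00001.

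It would have 84% power (futility ignored) only at a true HR of 1/0.58 = 1.72, which is harm.

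**Step 4. Against the futility rule.** Section 13.2 stops when the observed HR is above 1.0. Under the printed hypotheses, that is the region supporting H1. The plan would then stop for futility exactly when the data point towards the alternative.

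**Step 5. The intended success limit.** With H1: HR < 1 and 70 events, rejection needs an observed HR below exp(−2 × 1.2816/√70) = 0.736.

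**The case against.** The best reply is that the trial itself is not reversed; one displayed pair of inequalities is. Sections 13.2 and 13.3 make the intent plain, the 83% reproduces, and the link between Z < 0 and observed HR > 1 already implies that positive Z favours Arm A. On this view 0.0002 describes a test that nobody designed, and an analyst who reads the whole of Section 13 would not go wrong.

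That stands as to the design, and it makes the practical risk moderate. It does not rescue the text. No section redefines the HR as B to A. Both printed signs are reversed and agree with each other, so a single character misread from the PDF would not explain them. The Z convention is only implied, and a Cox Wald statistic for log HR(A/B) has the opposite sign, so the correct tail has to be inferred.

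Two limits on the numbers also stand:

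- **False success under harm.** At an illustrative true HR of 1.3 (a value assumed here, not in the plan), the printed test rejects with probability 1 − Φ(1.2816 − 0.2624 × 4.183) = 0.43. This ignores the interim look. If the non-binding stop is obeyed, the trial ends at 35 events about 78% of the time and the figure drops to about 1.5%.
- **HR cut-off.** The limit of 0.736 holds only at 70 events. Section 13.4 also allows the final analysis at a calendar limit of 12 months after last enrolment if that comes first. With 55 to 65 events (illustrative) the limit would be about 0.71 to 0.73.

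**Conclusion.** The concern holds. The primary hypotheses in Section 13.4 are reversed relative to the section's own definition of the HR, the design alternative, the power statement and the futility rule. Taken as printed, the probability of success at the planned effect is about 0.0002 in place of 83%. This rests on proportional hazards, equal allocation, 70 events and the usual normal approximation to the log-rank statistic. The error lies in the stated decision rule and not in the sizing: 88 patients, 70 events and one-sided alpha 0.1 give the claimed power once the direction is corrected. Because this is the formal rule for a one-sided primary test, it should be corrected before any analysis is run.

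**What to change.** In Section 13.4, replace the two lines with H0: HR ≥ 1 and H1: HR < 1, keeping HR as Arm A over Arm B. Add one sentence: a positive log-rank Z favours Arm A, and superiority is concluded if Z exceeds 1.2816 at the final analysis. This agrees with the Z < 0 futility rule in 13.2. If an HR equivalent is given, say that about 0.74 applies at 70 events and changes with the actual event count.

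Reversing the ratio to Arm B over Arm A would also work, but it means restating 0.58 as 1.73 and the futility condition as observed HR < 1, so changing the two signs is simpler. The cost is one or two lines of wording. Sample size, events, alpha, power and the interim boundary stay as they are.

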### **13.5 Analysis of Secondary Endpoints**

#### Efficacy Endpoints

All patients who initiated protocol therapy will be evaluated for PFS per irRECIST criteria, ORR, CBR, and OS. ORR and CBR will be evaluated using RECIST 1.1 and irRECIST criteria (as defined in Section 11.3). DOR will be evaluated among patients who had CR or PR. All these endpoints will be estimated separately in the two treatment arms.

The objective response rate (CR + PR) and immune-related response rate (irCR + irPR) will be reported by arm with 90% exact confidence intervals. Objective response rate and immune-related response rate will be compared between Arm A and Arm B, respectively using a Pearson

chi-squared test for difference in proportions with a one-sided  $\alpha$  of 0.1.

Clinical benefit is defined as CR, PR or SD  $\geq$  27 weeks. Clinical benefit will be calculated using RECIST 1.1 and irRECIST criteria, respectively. Clinical benefit rate (CR+PR+SD $\geq$ 27 wks) per RECIST 1.1 and irRECIST criteria will be reported respectively with 95% exact confidence intervals. CBR will be compared between two treatment arms using a Pearson chi-squared test for difference in proportions with a one-sided  $\alpha$  of 0.1.

PFS per irRECIST and OS will be also analyzed using Kaplan-Meier product-limit estimates and 95% confidence bands. PFS per irRECIST is defined as the time from study randomization to disease progression per irRECIST or death due to any cause, whichever occurred first. Patients alive without disease progression per irRECIST are censored at the date of last disease evaluation. OS is defined as the time from study randomization to death due to any cause. Patients will be censored at the date they were last known alive. The hazard ratio for each time-to-event endpoint will be estimated with 95% confidence intervals derived from the Cox proportional hazard model, but no hypothesis testing will be conducted.

DOOR is defined as the time from CR or PR achieved until renewed disease progression is detected. DOOR will be calculated per RECIST 1.1 and irRECIST criteria, respectively, and descriptive statistics will be used to summarize the intervals observed by arm.

In the group of patients treated with Pembrolizumab after progression on eribulin mesylate, CBR, PFS, OS, and DOOR after they received Pembrolizumab will be estimated using binomial, Kaplan-Meier and descriptive statistics, respectively with 95% confidence intervals. For this group, PFS and OS will start from the time of initiating Pembrolizumab. Under an assumption that approximately two-thirds of patients elect to cross over (n=30), the maximum width to an exact confidence interval for a proportion will be 0.374.

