### **Confirmation of Progressive Disease**

Pembrolizumab, like other immunotherapeutic agents, may produce antitumor effects by potentiating endogenous cancer-specific immune responses. The response patterns seen with such an approach may extend beyond the typical time course of image responses seen with cytotoxic agents, and can manifest as a clinical response after an initial increase in tumor burden

or even the appearance of new lesions.

For any subject who showed first radiologic evidence of progressive disease (PD) by RECIST 1.1 (see Section 11.1.4) and is deemed clinically stable, it is at the discretion of the investigator to continue treating the subject until progression is confirmed at least 4 weeks from the date of the first radiologic evidence of PD. If progression is confirmed, the subject will be discontinued from study treatment. Otherwise, the subject will continue treatment and radiographic scans. Any subject who had initial radiologic progression and is deemed clinically unstable should be discontinued from both study drugs and no subsequent scan for confirmation is required.

Further details are as below:

For purposes of PFS assessment on this trial, in addition to radiographic assessment of tumor response or progression, the investigator should into account the clinical condition/stability of subjects.

- Clinically stable is defined by the following criteria:
  - Absence of signs and symptoms (including worsening of laboratory values) indicating disease progression
  - No decline in ECOG performance status
  - Absence of rapid progression of disease
  - Absence of progressive tumor(s) at critical anatomical sites (eg, cord compression) requiring urgent alternative medical intervention

Any subject who showed first radiologic evidence of progressive disease and is deemed clinically unstable should be discontinued from both study drugs and is not required to have repeat imaging for confirmation.

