## **5.8 Duration of Follow Up**

Participants removed from protocol therapy for unacceptable adverse event(s) will be followed until resolution or stabilization of the adverse event.

In patients who come off trial for a reason other than progressive disease, if possible during the follow-up period, scans should be performed every 9 weeks (if the patients is within 27 weeks of

initiation of study treatment) or every 12 weeks (if the patient is greater than 54 weeks from initiation of study treatment) to evaluate for disease progression.

All participants will be followed annually by phone or by medical record until death.

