##### 11.3.1.1 Impact of New Lesions on irRECIST

New lesions in and of themselves do not qualify as progressive disease. However, their contribution to total tumor burden is included in the SPD which in turn feeds into the irRECIST criteria for tumor response. Therefore, new non-measurable lesions will not

discontinue any subject from the study.

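### irRECIST PFS has no rule for patients who stop for RECIST progression that is not irRECIST progression; censoring them at the last scan is informative and tends to lengthen the estimate

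*Combined protocol and SAP*

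**What the plan says.** Section 13.5 defines irRECIST PFS as the time from randomization to irRECIST progression or death, and adds: "Patients alive without disease progression per irRECIST are censored at the date of last disease evaluation". It will be reported with Kaplan-Meier estimates and a Cox hazard ratio with 95% confidence interval, without a test. It is the first secondary objective in Section 1.3.

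What counts as progression differs between the criteria. Under RECIST 1.1 (11.1.3.1 and 11.1.3.2), a new lesion or unequivocal non-target growth is progression. Under irRECIST, "New lesions in and of themselves do not qualify as progressive disease" (11.3.1.1), and 11.3.1.3 says the same of non-target growth until tumor burden has risen by 25%.

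Scanning after RECIST progression depends on the patient:

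- **Clinically unstable:** both drugs stop at first progression, and the patient "is not required to have repeat imaging for confirmation" (5.7; Section 10, note g).
- **Clinically stable:** treatment may continue, at the investigator's discretion, to a confirmatory scan at least 4 weeks later. If progression is not confirmed, treatment and scans go on. If it is confirmed, treatment ends unless an exception is agreed (5.7, 11.1).
- **Off treatment:** "In patients who come off trial for a reason other than progressive disease, if possible during the follow-up period, scans should be performed" (5.8; likewise Section 10, note i). Nothing is specified for those who stopped for progression.
- **Arm B crossover:** scans continue as scheduled (Section 10, note h). Section 13.5 expects about two-thirds of Arm B (n=30) to cross over.

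Survival is followed annually in everyone (5.8).

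**The concern.** Take a patient whose target lesions are nearly unchanged but who develops small new liver lesions at week 9, confirmed at week 13. Treatment stops for RECIST progression. Tumor burden has not risen by 25%, so there is no irRECIST progression, and no later scan is scheduled at which it could be recorded. If the patient is alive at the data cut, irRECIST PFS is censored at week 13. If the patient has died, the event is dated at death, perhaps many months later. Neither value is the time of irRECIST progression.

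Kaplan-Meier and Cox methods assume that a censored patient has the same future risk as those still followed. Here the patient is censored because the disease progressed, so the assumption fails in a known direction. A longer irRECIST PFS than RECIST PFS could then be read as immune-pattern disease control when part of the gap is missing scans. If missing scans are more common in one arm, the hazard ratio is affected as well.

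**Working it through.** **The plan's own figure.** The plan states no power, event count or median for irRECIST PFS. Its only related figure is the power for RECIST PFS: "83% power to distinguish a 3 month improvement in PFS from 4.1 to 7.1 months (HR = 0.58) with a one-sided alpha of 0.1"; this "assumes a final analysis when 70 PFS events are observed".

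- Schoenfeld: Φ(|ln(4.1/7.1)|·√(70/4) − 1.2816) = Φ(0.549 × 4.183 − 1.2816) = 84.5%.
- Freedman, with HR 0.5775: Φ(√70·(1 − HR)/(1 + HR) − 1.2816) = 83.1%.
- With the futility stop at Z < 0 after 35 events: 83.0%.
- Expected events with 44 per arm, 18 + 6 months and 5% yearly dropout: 38.3 + 31.7 = 69.9.

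The design reproduces, and this point does not touch it.

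**Which progressions are affected.** RECIST target progression needs +20% in the sum of diameters; irRECIST progression needs +25% in the sum of products. If both diameters grow alike, +20% gives 1.20² − 1 = +44%, and the 25% threshold is reached at √1.25 − 1 = +11.8% in diameter. RECIST progression from target growth is therefore normally irRECIST progression already. New measurable lesions also enter the sum of products. What remains is progression through non-target growth, non-measurable new lesions, or new measurable lesions too small to reach the threshold.

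**Size.** This is a simulation with 400,000 patients per setting.

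- From Section 13.2: RECIST PFS medians of 4.1 and 7.1 months, and "constant accrual over 18 months with 6 months of additional follow-up".
- Assumed, not in the documents: exponential times; f, the share of RECIST progressions that are not irRECIST progression at that scan; c, the share of those still scanned until irRECIST progression; a median lag of 2.1 months to irRECIST progression (about one 9-week scan interval); median survival after RECIST progression of 9 months. Dropout is not modelled.
- Rule as written: an affected patient is an event at death if death precedes the cut; otherwise censored at the RECIST progression scan.
- Benchmark: the irRECIST median had every patient been scanned to irRECIST progression.

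Medians in months at c = 0 (no further scans):

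| Arm | f | Complete scanning | As written | Inflation |
|---|---|---|---|---|
| Control | 10% | 4.36 | 4.57 | 5% |
| Control | 30% | 4.92 | 5.76 | 17% |
| Control | 50% | 5.44 | 7.26 | 33% |
| Combination | 10% | 7.39 | 7.78 | 5% |
| Combination | 30% | 7.93 | 9.29 | 17% |
| Combination | 50% | 8.50 | 11.06 | 30% |

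Inflation is (as written ÷ complete) − 1; for example 5.76/4.92 − 1 = 17%.

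- c = 0.5: about 2%, 8% and 14% at f = 10%, 30% and 50%, in either arm. At c = 1 or f = 0 there is none.
- Lag of 1 month, c = 0: 7% to 51%. Lag of 4 months, c = 0: 2% to 19%.
- At c = 0, the affected patients by the cut are 9%, 27% and 44% of the control arm and 7%, 22% and 37% of the combination arm. About half of them (49% to 53%) have died by then and are late events, not censorings.

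**Effect of crossover on the hazard ratio.** The model uses the same f in both arms, c = 0 in Arm A and 9-month survival. With complete scanning the irRECIST hazard ratio is about 0.59. If two-thirds of Arm B cross over and their scans count, it moves to about 0.56, 0.54 and 0.49 at f = 10%, 30% and 50%, in favor of the combination. If crossover scans do not count, it barely moves but both medians are inflated.

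**The case against.** The strongest reply is that the problem is narrower than it looks, and most of that reply stands.

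- A reader might infer that scans stop at RECIST progression for everyone. They do not: stable patients may be rescanned or continue, and crossover patients keep their schedule. Only clinically unstable patients are exempted from the repeat scan. The confirmatory scan does not remove the gap, though, because confirmation normally ends both treatment and scheduled scans.
- A reader might infer that all patients who stop for progression are censored. Target-growth progressors are already irRECIST events, and discordant patients who die are events, though late ones.
- A reader might measure the bias against 4.1 and 7.1 months. Those are RECIST assumptions, and irRECIST PFS is meant to be longer. At f = 30% the control median rises from 4.11 to 5.76, or 40%. Of that, 4.11 to 4.92 (20%) is the genuine difference between criteria, and only 4.92 to 5.76 (17%) is bias.
- A reader might infer equal inflation in both arms. Continued crossover scans make Arm B different if they count, and the plan leaves that open.
- Making a stop for RECIST progression the main event is not a clean cure. At c = 0 it returns the medians to 4.1 and 7.1, which largely turns the endpoint into RECIST PFS. It would also end follow-up at crossover although scans are still collected.

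**Conclusion.** The concern holds in a limited form. Section 13.5 does not address patients who stop for RECIST progression without irRECIST progression, and the schedule specifies no further scan for them outside crossover. Applying the rule as written gives informative censoring or late death events, and an upward tendency in irRECIST PFS.

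The documents do not fix the size. With 9-month survival after progression, a 2.1-month lag and no further scans, the inflation of the median is about 5% to 33% for 10% to 50% discordant progressions. It is roughly half that or less if half of these patients are still scanned, and nil if all are. The hazard ratio may be biased too. In the case modelled the bias favors the combination if crossover scans count, but a different discordant share by arm could change its direction.

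The consequence is moderate: the endpoint is secondary and estimated without a test, and the primary RECIST PFS analysis and its power are unaffected.

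**What to change.** In Section 13.5:

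1. Keep the current irRECIST PFS definition.
2. Add a pre-specified sensitivity analysis in which permanent stop of randomized treatment for progression (RECIST or clinical), with no later scan, is an event at the progression date.
3. State whether scans during Arm B crossover count toward irRECIST PFS. If they do, state which baseline and nadir apply, since Section 13.1 resets the baseline for the separate crossover analysis.
4. Report by arm how many patients stopped for RECIST progression without irRECIST progression, and how many of those had a later scan.

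The cost is a few sentences and some programming. No extra scans are needed, because Section 5.7 already requires the reason and date of removal from therapy to be recorded. The downside is that the sensitivity version is conservative, since it moves toward RECIST PFS. Read beside the current definition, it shows how far the irRECIST result depends on missing scans.
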